9 ASSESSMENT OF INVESTIGATIONAL MEDICINAL PRODUCT

The assessments will be performed according to the schedule presented in the Study Flowchart. See [Section 1.2](#) and [Section 10](#) for further details.

9.1 PRIMARY ENDPOINT

9.1.1 Primary efficacy endpoint

The primary endpoint is the number of new or enlarging T2 lesions on brain MRI, during continuation of prior DMT (Period 1) compared to an equal period after the first course of alemtuzumab treatment (Period 2). The primary efficacy endpoint will be assessed by brain MRI.

9.1.1.1 Brain MRI

For primary endpoint assessment, two periods have been defined

- **Period 1:** will occur from M-4 up to M0. An MRI will be performed during the screening period and another at Visit 3. Both MRI will be taken while patients are on their prior DMT. The two MRIs will be compared by a central assessor to count the number of new or enlarging T2 lesions. It is important to ensure that these 2 MRI assessments are performed 4 months (± 7 days) apart.
- **Period 2:** will occur from M4 to M8: The MRI performed at the M4 visit will be the baseline MRI for Period 2. A second MRI will be performed after alemtuzumab first course of treatment at M8. The two MRIs will be compared by a central assessor to count the number of new or enlarging T2 lesions. It is important to ensure that these 2 MRI assessments are performed 4 months (± 7 days) apart.

It is expected that Periods 1 and 2 will be of the same length ± 7 days.

“Baseline” MRI will be collected during the screening visit (baseline for Period 1) and the M4 visit (baseline for Period 2). The “baseline” lesion volume for the corresponding period will be adjusted in the generalized estimating equation (GEE) model.

Screening MRI is expected to be reviewed locally by PI only for study eligibility confirmation. The MRI assessments will also be available to the investigators to assess safety.

In addition to primary endpoint MRIs (Screening, D-7, M4, M8) other MRIs will be performed at M12, M24/at EOTP, and then annually in the Safety Monitoring Phase.

All brain MRIs will be reviewed and interpreted by one or more MRI experts at an independent, central facility with no access (ie, blinded) to patients’ treatment thereby avoiding bias.

An MRI manual explaining the instructions for standard image acquisition requirements, data transfer, archiving and shipping, and outlining the phantom data approval process will be provided to all centers.

MRI should not be conducted within 2 weeks of steroid administration due to potential interference with MRI assessment.

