6 STUDY DESIGN

6.1 DESCRIPTION OF THE STUDY

This is an open-label, rater-blinded, single-arm, before and after switch study of efficacy, safety and tolerability of alemtuzumab in paediatric patients from 10 to <18 years of age with RRMS with disease activity on prior DMT.

The study will consist of:

- **Screening period** (0-28 days prior to M-4) - Patients and parents will receive information on the study and on alemtuzumab. Inclusion/exclusion criteria will be reviewed. After informed consent signature, screening assessments for eligibility will be performed. Screening assessments may require more than one visit within the screening period which may last a maximum of 28 days.
- **Prior DMT phase (approximately 4 months): M-4 to M0**
 - **Eligibility confirmation visit:** At the end of the screening period (at M-4) patients/parents will come to the site to confirm patient is eligible for the study. Investigator will check that all assessment allow patient inclusion. During this visit patients will be reminded to continue their prior DMT (limited to interferon or GA only).
 - **From M-4 visit to D-14 to D-7:** Phone calls (approximately every month) will be done, to remind patients to continue on their DMT and check patient status.
 - **Day -14 to D-7 visit:** Investigator will confirm patient is eligible for alemtuzumab administration and will tell the patient to discontinue current DMT 7 days prior to administration of first dose of alemtuzumab at Month 0.
- **Alemtuzumab treatment phase** (approximately 2 years) – This phase starts with administration of first dose of alemtuzumab at M0, after discontinuation of current DMT, and ends at M24. The second dose of alemtuzumab will be administered at M12. The MRI based primary efficacy endpoint will be assessed over a 4 month period during this phase compared to an equal period during the prior DMT phase.

Note: end of treatment phase (EOTP) refers to the end of the alemtuzumab treatment phase (see graphic study design [[Section 1.1](#)]).
- **Safety monitoring phase** (approximately 3 years) – Additional safety follow-up and monitoring for all patients treated with alemtuzumab will be conducted during this phase to yield a total of 5 years of follow-up since first alemtuzumab treatment, including 4 years post last treatment with alemtuzumab.

Note: end of study (EOS) refers to the end of the safety monitoring phase (see graphic study design [[Section 1.1](#)]).

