11.1 DETERMINATION OF SAMPLE SIZE

At least 60 patients aged from 10 years to less than 18 years will be screened in this study to account for screen failures, to ensure that at least 50 patients are evaluable. According to the means and variability reported in other paediatric MS studies (17), it was assumed that there is an average of 9 new or enlarging T2 lesions during continuation of prior DMT (Period 1) and an overdispersion parameter of 0.7 for both study periods. Further assuming a conservative within-person correlation of 0.25 for the lesion counts, a 10% dropout rate, and a two-tailed significance level of 0.05, this sample size will provide at least 85% power to detect a 50% reduction in the number of new or enlarging T2 lesions after the first course of alemtuzumab (Period 2) compared to the equal-length Period 1. These sample size calculations were simulated using a correlated, repeated measures negative binomial regression model with GEE with robust variance estimation to account for the within-patient correlation in lesion counts between treatment Period 1 (prior DMT) and Period 2 (alemtuzumab).

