11.4 STATISTICAL METHODS

Analyses for the primary and secondary efficacy endpoints will be conducted using the mITT population. Analyses for the safety endpoints will be conducted using the safety population. Analyses for the PD endpoints will be conducted using the PD populations. Analyses for the PK endpoints will be conducted using the PK populations. Analyses for the exploratory endpoints will be conducted using the safety population.

In the descriptive analyses, summary statistics for continuous variables will minimally include n, mean, standard deviation (SD), minimum, median, and maximum. For categorical variables, frequencies and percentages will be presented. Graphical displays will be provided as appropriate.

Unless otherwise specified, all baseline values will be defined as the last nonmissing value prior to the first course of alemtuzumab.

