11.4.2.1 Analysis of primary efficacy endpoint

The number of new or enlarging T2 lesions during continuation of prior DMT (Period 1) and in an equal-length period after the first course of alemtuzumab treatment (Period 2) will be analyzed and compared using a repeated measures negative binomial regression model with GEE. The default log link function will be used to model the expected number of lesions. The robust, sandwich covariance matrix will be constructed assuming an unstructured/exchangeable working correlation matrix.

The primary statistical objective is to test superiority of alemtuzumab versus prior DMT at 5% level of significance. No missing data is expected as the mITT population is restricted to the patients with evaluable data for both Period 1 and Period 2.

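### The primary GEE adjusts Period 2 for a lesion volume measured four months after alemtuzumab, and the analysis section states the model without that covariate

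*Protocol*

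**What the plan says.** Protocol section 9.1.1.1 defines two baselines for the primary endpoint: "MRI will be collected during the screening visit (baseline for Period 1) and the M4 visit (baseline for Period 2"). It then puts the volume from each into the primary model: baseline "lesion volume for the corresponding period will be adjusted in the generalized estimating equation (GEE) model".

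Section 6.1 fixes the start of alemtuzumab: "This phase starts with administration of first dose of alemtuzumab at M0, after discontinuation of current DMT, and ends at M24". The M4 scan therefore falls about four months after the first course.

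Section 11.4.2.1 says the lesion counts in the two periods "will be analyzed and compared using a repeated measures negative binomial regression model with GEE". It gives the log link and adds: "The robust, sandwich covariance matrix will be constructed assuming an unstructured/exchangeable working correlation matrix". It names no covariate. Neither does the synopsis, nor section 11.1, which says of the power figure: "These sample size calculations were simulated using a correlated, repeated measures negative binomial regression model with GEE with robust variance estimation".

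Section 11.4 has a default that applies unless something else is specified: "all baseline values will be defined as the last nonmissing value prior to the first course of alemtuzumab". M4 is not such a value.

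**The concern.** The covariate differs between the two periods within each patient, and its Period 2 value can be altered in two ways. Alemtuzumab can change it between M0 and M4. Lesions already counted in Period 1, and those arising between M0 and M4 that neither period counts, can remain in it.

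In a one-sequence before/after comparison, any mean change in such a covariate is aligned with the period contrast, so adjusting for it is not a simple gain in precision. The coefficient moves away from the endpoint in section 9.1.1, which compares the lesion counts of the two periods.

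This is the only formally tested model in the trial (sections 11.4.2.1 and 11.4.2.3). The reported rate ratio, and the error rate near the null, would depend partly on how lesion volume moved by M4. Because section 11.4.2.1 does not carry the adjustment, a reader also cannot tell from the analysis section which model is primary. The comparison of patients with and without lesions (section 11.4.2.2) is modelled on the primary analysis and inherits the doubt.

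**Working it through.** **1. Order of events (sections 6.1 and 9.1.1.1)**

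| Time point | Role in the primary analysis |
|---|---|
| Screening scan | Opens Period 1; covariate for Period 1 |
| Visit 3 scan (D-14 to D-7) | Closes Period 1 |
| M0 | First alemtuzumab course |
| M4 scan | Opens Period 2; covariate for Period 2 |
| M8 scan | Closes Period 2 |

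The M4 scan comes before the Period 2 counting window, so it does not overlap its own outcome. It does follow both treatment and the Period 1 outcome.

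**2. The Protocol's own figure.** Section 11.1 gives a Period 1 mean of 9, a 50% reduction (mean 4.5), overdispersion 0.7, correlation 0.25, 10% dropout and two-sided 0.05. Taking 50 patients less 10% gives n = 45. Without a covariate,

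Var(log ratio) = [v1/m1² + v2/m2² − 2ρ√(v1·v2)/(m1·m2)]/n, and power = Φ(ln 2/SE − 1.96).

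- With v = m + m²/0.7: (1.540 + 1.651 − 0.797)/45 = 0.0532, SE 0.231, power 85.2%.
- With v = m + 0.7m²: (0.811 + 0.922 − 0.432)/45 = 0.0289, SE 0.170, power 98.3%.

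Both meet the stated 85% or more, and both come from the model without lesion volume.

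**3. Closed form for the shift.** Let the fitted model be log E(count) = a + δ·period + β·log(volume). Then approximately

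δ = log(true ratio) − β × (mean log volume at M4 − mean log volume at screening).

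The estimated ratio is thus multiplied by (volume M4/volume screening)^−β. The volume changes and β below are assumptions.

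| β | Volume −20% | Volume +30% |
|---|---|---|
| 0 | 1.00 | 1.00 |
| 0.3 | 0.8^−0.3 = 1.07 | 1.3^−0.3 = 0.92 |
| 0.6 | 0.8^−0.6 = 1.14 | 1.3^−0.6 = 0.85 |

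A rise in volume moves the result towards alemtuzumab and a fall moves it against.

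**4. Simulation at the trial's size.** Negative binomial GEE, log link, robust standard errors, 45 patients, 30 scenarios per true ratio, 1000 runs each. The mean, overdispersion (0.7) and correlation are from section 11.1, except that the correlation is about 0.4 where β = 0.6 forces it. Assumed: median volume 6 mL, log-SD 0.9; count rate proportional to screening volume to the power 0, 0.3 or 0.6; covariate entered as log or raw volume; M4 volume unchanged, or raised by 0.05 or 0.10 mL per earlier lesion, or raised by 0.05 mL per lesion and then shrunk by 10% or 25%; M0–M4 lesion rate midway between the two periods. Mean log volume at M4 then corresponded to 0.84 to 1.37 times screening.

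| | M4 volume in Period 2 | Screening volume in both periods |
|---|---|---|
| Estimate, true ratio 1 | 0.865–1.107 | 0.985–1.012 |
| Significant for alemtuzumab (nominal 2.5%) | 0.2–19.1% | 2.5–4.8% |
| Significant against (nominal 2.5%) | 0.1–13.1% | 2.2–4.7% |
| Estimate, true ratio 0.5 | 0.441–0.557 | 0.495–0.505 |

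The unadjusted estimate at a true ratio of 1 is 0.986–1.013. Where volume does not predict counts, the M4-adjusted estimate is 0.995–1.010. At a true ratio of 0.5, rejection is 96–100% in every scenario. The closed form matches: 1.267^−0.62 = 0.864 against 0.865 simulated, and 0.852^−0.61 = 1.103 against 1.107. With N = 3000 the ranges stay at 0.860–1.112 and 0.436–0.561, so the shift does not vanish with sample size. Exchangeable and independence working correlations differ by at most 0.008.

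**5. A check under a different mechanism.** Here Period 2 counts depend on the M4 volume itself, with the total ratio held at 0.50 (40,000 patients; assumed slope 0.25 to 1.0 per SD of log volume, mean change −0.30 to +0.30 SD). Screening adjustment returns 0.49–0.51. M4 adjustment returns 0.54–0.65 at −0.30 SD, about 0.50 at no change, and 0.37–0.47 at +0.30 SD.

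**The case against.** Four points deserve weight.

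- Section 11.4.2.1 is silent on covariates and does not exclude them. It can be read together with section 9.1.1.1 as one adjusted model, and covariate detail is often left to the SAP. That softens the disagreement to a mismatch between a section that fixes an adjustment and an analysis section that omits it. The problem with the M4 covariate remains, because the Protocol itself fixes it.
- The baseline rule in section 11.4 yields where something else is specified, and section 9.1.1.1 does specify. There is no conflict there.
- Part of the M4 volume is accrual before M0, which is disease burden and not a treatment effect. A comparison conditional on burden at the start of each period can be defended, but it is a different estimand from the stated endpoint.
- The simulation in step 4 lets counts depend on screening volume, which favours screening adjustment. Step 5 removes that advantage, and the M4-adjusted coefficient still departs from the total before/after ratio.

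It also stands that every volume figure is assumed, and that the widest shifts need the steepest assumed slopes.

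**Conclusion.** The concern holds. As written, the primary model contains a covariate that is measured after treatment and varies within patient, and the analysis section describes the model without it.

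The shift in the log ratio is about −β times the mean change in the covariate. It is nil if volume does not predict counts or does not change. Its actual size and direction cannot be derived from the Protocol. Under the assumed volumes, a true ratio of 1 is estimated at 0.865 to 1.107, and one-sided false-positive rates in favour of alemtuzumab run from 0.2% to 19.1%. A small part of the excess over 2.5% is a small-sample effect, since screening adjustment also reaches 4.8%.

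Detection of the planned 50% reduction is unlikely to be lost. The 96–100% rejection rates were run at 45 patients with overdispersion 0.7; under the m²/0.7 reading, where power starts at about 85%, the margin is smaller. The stated power is not affected, as it rests on the model without a covariate. The point should be fixed because it governs how the reported ratio can be read.

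**What to change.** Replace the adjustment sentence in section 9.1.1.1 by: *The screening (pre-alemtuzumab) lesion volume, one value per patient, will be included as a covariate in both periods.* State the same model in section 11.4.2.1 and in the synopsis.

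Name the screening scan explicitly. The default baseline in section 11.4 would otherwise select the Visit 3 scan, which closes Period 1 and so already contains its outcome. Keep any model with M4 volume as a supportive analysis only.

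Dropping the covariate altogether gives nearly the same ratio. Screening volume is preferred because it retains an adjustment for lesion burden.

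The cost is one sentence in each of three places and no new data, since the screening scan is already part of the schedule. The downside is that the primary model no longer adjusts for lesion burden at the start of Period 2; the supportive analysis covers that.

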9.2 SECONDARY ENDPOINTS

Secondary endpoints include the efficacy, quality of life and pharmacokinetic/Pharmacodynamic endpoints are listed below, and will be assessed as shown in [Section 9.2.1](#) and [Section 9.2.2](#):

Efficacy:

- The number of patients with new or enlarging T2 lesions during continuation of prior DMT (Period 1) compared to an equal period after the first course of alemtuzumab treatment (Period 2).
- EDSS (descriptive analysis, ie percentages of stable/improved/worsened since the end of Period 1).
- Annualized relapse rate (ARR) at Year 2.
- Cognition test scores: Brief Visuospatial Memory Test – Revised (BVMT-R) and Symbol Digit Modality Test (SDMT); administered at least every 6 months over 2 years.

Quality of life:

- Established generic paediatric QoL measures administered every 6 months over 2 years.

Pharmacokinetics/Pharmacodynamics:

- PK serum concentration and PK parameters (C_{max} , T_{max} , AUC, AUC_{last} , $T_{1/2z}$) calculated where possible.
- PD assessment including lymphocyte subsets.

9.2.1 Secondary efficacy endpoints

9.2.1.1 Expanded disability status scale

Patient disability will be evaluated using the EDSS ([Appendix D](#)), which has long been considered the standard for assessing disability in patients with MS ([19](#)).

The EDSS is an ordinal clinical rating scale which ranges from 0 (normal neurologic examination) to 10 (death due to MS) in half-point increments. Briefly, the assessing neurologist rates 7 functional systems (pyramidal, cerebellar, brainstem, sensory, bowel and bladder, visual ratings) in conjunction with observations and information concerning the patient's mobility, gait, and use of assistive devices to assign an EDSS score.

EDSS steps 1.0 to 4.5 refer to people with MS who are fully ambulatory, while EDSS steps 5.0 to 9.5 are defined by the impairment to ambulation.

The EDSS will be performed by the neurologist at the following visits: Screening, D-7, M4, M8, M12, M15, M18, M21, M24/at EOTP; every 6 months in Safety Monitoring Phase, and at every relapse visit.

9.2.1.2 Annualized relapse rate at Year 2

Subjects/parents/guardians will be instructed to contact their Investigator immediately should any symptoms suggestive of an MS relapse appear. The subject must be examined as soon as possible, within 7 days from the onset date of the relapse.

Relapses are defined as new or recurrent neurological symptoms not associated with fever or infection, lasting at least 24 hours, and accompanied by new objective neurological findings upon examination by the neurologist and documented by the functional system scores. The subject must have objective signs on the neurologist's examination confirming the event.

New or recurrent symptoms that occur less than 30 days following the onset of a relapse should be considered part of the same relapse. The Investigator can, at his/her discretion, treat the patient with corticosteroids.

Relapses will not be considered as AEs (see AE [Section 10.4.3](#)).

9.2.1.3 Cognition test scores

9.2.1.3.1 Brief visuospatial memory test - revised

The Brief Visuospatial Memory Test - Revised (BVMT-R) is a commonly used, commercialized, assessment tool to measure visuospatial learning and memory abilities across research and clinical settings.

A visual display of six simple figures arranged in a 2 × 3 matrix on separate pages is shown to participants/patients for three consecutive 10-second trials. After each trial, participants are to draw as many designs as accurately as they can and in the correct location. They are again asked to reproduce the designs in the exact layout after a 25-minute delay filled with other distractor tasks. A forced-choice recognition trial is administered immediately following the delayed memory trial. An optional copy trial is included at the end of the test where the participants are asked to copy the figure display as accurately as they can. Scoring of the immediate and delayed recall as well as copy trials are based on the accuracy of the drawings and the location of the figures. For each figure, one point is awarded to each satisfactory domain resulting in a maximum of 12 points per trial.

Brief Visuospatial Memory Test-Revised will be assessed at Screening, D-7, M4, M8, M12, M18, M24/at EOTP; annually in Safety Monitoring Phase. Central scoring will be performed by an independent rater who is blinded to treatments (ie, current DMT or alemtuzumab).

9.2.1.3.2 Symbol digit modality test

Cognitive impairment will be assessed using the Symbol Digit Modality Test (SDMT) Brief and easy to administer, the SDMT has demonstrated remarkable sensitivity in detecting not only the presence of brain damage, but also changes in cognitive functioning over time and in response to treatment. The SDMT involves a simple substitution task that normal children and adults can easily perform. Using a reference key, the examinee has 90 seconds to pair specific numbers with given geometric figures. Responses can be written or oral, and for either response mode, administration time is just 5 minutes. For this study, only ORAL form of response is desired (ie, patient does NOT write down the responses, instead, patient is instructed to verbally call out the numbers that correspond to the symbols and the administer writes down his/her responses.

9.2.2 Other secondary endpoints

9.2.2.1 Pharmacokinetics

For patients receiving alemtuzumab, serum concentrations and PK parameters will be studied

9.2.2.1.1 Sampling time

The sampling times for blood collection can be found in the Study Flow Chart [Section 1.2.4](#) and [Section 1.2.5](#).

9.2.2.1.2 Pharmacokinetics handling procedure

Special procedures for collection, storage, and shipment of plasma samples collected for EFC13429 concentrations will be provided in a separate laboratory manual.

9.2.2.1.3 Bioanalytical method

Details of the bioanalytical methods are described in [Appendix B](#) and detailed in a separate laboratory manual.

9.2.2.1.4 Pharmacokinetics parameters

The following PK parameters will be calculated, using noncompartmental methods from the cumulative serum alemtuzumab concentrations. The parameters will include, but may not be limited to the following [Table 8](#):

Table 8 - List of pharmacokinetic parameters and definitions

Parameters	Drug/Analyte	Matrix	Definition/Calculation
C _{max}	Alemtuzumab	Serum	Maximum serum concentration observed
T _{max}	Alemtuzumab	Serum	Time to reach C _{max}
AUC _{last}	Alemtuzumab	Serum	Area under the cumulative serum concentration versus time curve calculated using the trapezoidal method from time zero to the real time t _{last}
	Alemtuzumab	Serum	Area under the cumulative serum concentration versus time curve extrapolated to infinity according to the following equation:
AUC			$AUC = AUC_{last} + \frac{C_{last}}{\lambda_z}$
	Alemtuzumab	Serum	Values with percentage of extrapolation >30% will not be reported
t _{1/2z}			Terminal half-life associated with the terminal slope (λ _z) determined according to the following equation:
			$t_{1/2z} = \frac{0.693}{\lambda_z}$
			where λ _z is the slope of the regression line of the terminal phase of the cumulative serum concentration versus time curve, in semi-logarithmic scale. Half-life is calculated by taking the regression of at least 3 points.

